5.4.2 Growth Factor Therapy

Growth factors may be administered in accordance with American Society of Clinical Oncology Guidelines [17]. Dosing of abemaciclib must be suspended if the administration of growth factors is required and must not be restarted within 48 hours of the last dose of growth factors having been administered. When restarted, the dose of abemaciclib must be reduced by 1 dose level if a dose reduction for the specific event necessitating the use of the growth factors has not already occurred.

5.4.3 Supportive Management for Diarrhea

At enrollment, patients should receive instructions on the management of diarrhea. In the event of diarrhea, supportive measures should be initiated as early as possible. These include the following:

- At the sign of loose stools, patients should initiate anti-diarrheal therapy (for example, loperamide) and notify the investigator/site for further instructions and appropriate follow-up.
- Participants should be encouraged to drink fluids (for example, 8 to 10 glasses of clear liquids per day)
- Site personnel should assess response within 24 hours
- If diarrhea does not resolve with anti-diarrheal therapy within 24 hours to either baseline or Grade 1, study drug should be held until diarrhea is resolved to baseline or grade 1.
- If diarrhea resolves to baseline or grade 1, participants should resume dosing as outlined in Section 6.3.2 and Table 6.1.

In severe cases of diarrhea, measuring neutrophil counts and body temperature and proactively managing diarrhea with antidiarrheal agents is recommended (page 16). In addition, patients with \geq grade 3 diarrhea should be reviewed by a treating physician once per week until the diarrhea has resolved to \leq grade 1.

If diarrhea is severe (requiring IV rehydration) and/or associated with fever or severe neutropenia, broad-spectrum antibacterial therapy, including coverage for enteric (gram-negative and anaerobic) bacteria. If neutropenic fever persists for 5 days despite broad-spectrum antibacterial therapy, empiric antifungal therapy should be initiated. If diarrhea persists after antibiotic treatment, testing for *Clostridium difficile* is indicated as antibiotic therapy might precipitate *C. difficile* infection.

Patients with severe diarrhea or any grade of diarrhea associated with severe nausea or vomiting should be carefully monitored and given IV fluid (IV hydration) and electrolyte replacement. In these patients, electrolytes and renal function should be monitored regularly during the period of IV hydration.

5.5 Criteria for Taking a Participant Off Protocol Therapy.

Duration of therapy will depend on individual response, evidence of disease progression and tolerance. In the absence of treatment delays due to adverse event(s), treatment may continue until one of the following criteria applies:

- Disease progression
- Intercurrent illness that prevents further administration of treatment
- Unacceptable adverse event(s)
- Participant demonstrates an inability or unwillingness to comply with the oral medication regimen and/or documentation requirements
- Participant decides to withdraw from the protocol therapy
- General or specific changes in the participant's condition render the participant unacceptable for further treatment in the judgment of the treating investigator

Participants will be removed from the protocol therapy when any of these criteria apply. The reason for removal from protocol therapy, and the date the participant was removed, must be documented in the case report form (CRF) and in the clinical trial management system, OnCore. Alternative care options will be discussed with the participant.

In the event of unusual or life-threatening complications, treating investigators must immediately notify the overall PI, [name] at [contact].

5.6 Duration of Follow Up

Participants should remain in long-term follow-up with disease status and overall survival status checked once every 6 months until death. There are no long-term follow-up visits required.

Participants removed from protocol therapy for unacceptable adverse event(s) will be followed until resolution or stabilization of the adverse event.

5.7 Criteria for Taking a Participant Off Study

Participants will be removed from study when any of the following criteria apply:

- Lost to follow-up
- Withdrawal of consent for data submission
- Death

The reason for taking a participant off study, and the date the participant was removed, must be documented in the case report form (CRF) and updated with the relevant Off Treatment/Off Study information in OnCore.

6. DOSING DELAYS/DOSE MODIFICATIONS

6.1 Dose Adjustments and Delays

Table 6.1 Toxicity Dose Adjustments and Delays for Abemaciclib

Toxicity Type	Toxicity Profile and Severity	Dose	
Hematologic Toxicity Sections 6.2 and 5.4.2	Requiring administration of growth factors, regardless of severity (Growth factors use permitted according to ASCO Guidelines)	Dose MUST be suspended for at least 48 hours after the last dose of blood cell growth factors was administered and until toxicity resolves to at least Grade 2.	Dose MUST be reduced by 1 dose level unless already performed for incidence of toxicity that lead to the use of growth factor.
Hematologic Toxicity Section 6.2	Grade 3	Dose MUST be suspended until toxicity resolves to at least Grade 2.	Dose MAY be reduced by 1 dose level - investigator's discretion.
Hematologic Toxicity Section 6.2	Recurrent Grade 3	Dose MUST be suspended until toxicity resolves to at least Grade 2.	Dose MUST be reduced by 1 dose level.
Hematologic Toxicity Section 6.2	Grade 4	Dose MUST be suspended until toxicity resolves to at least Grade 2.	Dose MUST be reduced by 1 dose level.
Non-hematologic Toxicity (except diarrhea and increased AST/ALT) Section 6.3	Persistent or recurrent Grade 2 that does not resolve with maximal supportive measures within 7 days to baseline or Grade 1	Dose MUST be suspended until toxicity resolves to either baseline or Grade 1.	Dose MUST be reduced by 1 dose level
Non-hematologic Toxicity (except diarrhea and increased AST/ALT) Section 6.3	Grade 3 or 4	Dose MUST be suspended until toxicity resolves to either baseline or	Dose MUST be reduced by 1 dose level.

		Grade 1.	
Diarrhea Sections 6.3.2 and 5.4.3	Grade 2	Dose MUST be suspended if toxicity does not resolve within 24 hours to \leq Grade 1.	Dose reduction is not required.
Diarrhea Sections 6.3.2 and 5.4.3	Persistent or recurrent Grade 2 that does not resolve with maximal supportive measures within 24 hours to at least Grade 1	Dose MUST be suspended until toxicity resolves to at least Grade 1.	Dose MUST be reduced by 1 dose level - investigator's discretion.
Diarrhea Sections 6.3.2 and 5.4.3	Diarrhea recurs despite maximal supportive measures after resuming same dose level after initial Grade 2 diarrhea	Dose MUST be suspended until toxicity resolves to at least Grade 1.	Dose MUST be reduced by 1 dose level.
Diarrhea Sections 6.3.2 and 5.4.3	Requires hospitalization or Grade 3 or 4	Dose MUST be suspended until toxicity resolves to at least Grade 1.	Dose MUST be reduced by 1 dose level.
Hepatic Toxicity (AST and/or ALT) Section 6.3.4	Persistent or recurrent Grade 2 ($> 3.0-5.0 \times$ ULN) OR Grade 3 ($>5.0-20.0 \times$ ULN) that does not resolve with maximal supportive measures within 7 days to baseline or Grade 1	Dose MUST be suspended until toxicity resolves to baseline or Grade 1.	Dose MUST be reduced by 1 dose level.
Hepatic Toxicity (AST and/or ALT) Section 6.3.4	Grade 3 ($>5.0-20.0 \times$ ULN) AND Total Bilirubin $> 2.0 \times$ ULN, in the absence of cholestasis.	Discontinue Abemaciclib.	N/A
Hepatic Toxicity (AST and/or ALT) Section 6.3.4	Grade 4 ($>20.0 \times$ ULN)	Discontinue Abemaciclib.	N/A

Abbreviation: ASCO = American Society of Clinical Oncology.

Note: MAY = per the investigator's clinical judgment; SHOULD = not mandatory but highly recommended; MUST = mandatory.

6.1.1 Abemaciclib Dose Adjustments

If a patient who, in the judgment of the investigator, is receiving clinical benefit from study therapy requires further dose reduction than is outlined in Table 6.1, then the investigator must discuss with the PI prior to any further dose reduction. For patients requiring dose reduction(s), re-escalation to a prior dose level is permitted only after consultation with the PI.

A cycle is defined as the planned treatment interval of 28 days plus any subsequent delay prior to start of the next cycle. A delay in the start of a cycle due to holidays, weekends, bad weather, or other unforeseen circumstances will be permitted up to 7 days and not counted as a protocol deviation. No more than 56 doses of abemaciclib should be dispensed for each 28-day cycle. Dose omissions are allowed within a cycle. If a patient requires omission of more than 25% of doses during a cycle for tolerability, then treatment may continue if the investigator determines

the patient is receiving clinical benefit.

Table 6.1.1 Dose Adjustments of Abemaciclib

Dose Adjustment	Oral Dose	Frequency
0	200 mg	Every 12 hours
1	150 mg	Every 12 hours
2	100 mg	Every 12 hours
3	50 mg	Every 12 hours

6.2 Hematologic Toxicity

Hematologic toxicities including neutropenia, leukopenia, anemia, and thrombocytopenia have been observed in patients treated with abemaciclib, and causality has been established. Patients should be monitored closely for signs of infection, anemia, and bleeding. Dose adjustment may be considered for hematological toxicity \geq Grade 3. Hematological toxicities must resolve to baseline or at least Grade 2 prior to the start of each cycle. Blood cell growth factors are only to be used in a manner consistent with American Society of Clinical Oncology (ASCO) guidelines. Fever or infection in the presence of severe neutropenia should be managed promptly with broad-spectrum antibacterial therapy, including coverage for enteric (gram-negative and anaerobic) bacteria. If neutropenic fever persists for 5 days despite broad-spectrum antibacterial therapy, empiric antifungal therapy should be initiated. Anemia and thrombocytopenia should be treated supportively and if necessary with red cell or platelet transfusions.

Tables 6.1 and 6.1.1 provide further detail on abemaciclib dose modification for hematologic toxicity.

6.3 Non-hematologic Toxicity

6.3.1 Dose adjustment for other non-hematologic toxicity (other than diarrhea)

Before the start of each cycle, non-hematologic toxicity must be evaluated. All non-hematologic toxicities (except alopecia, diarrhea and fatigue) possibly related to abemaciclib must resolve to either baseline or at least Grade 1.

If a patient experiences persistent or recurrent Grade 2 non-hematologic toxicity (except diarrhea; refer to Section 6.3.2) possibly related to abemaciclib that does not resolve with maximal supportive measures within 7 days to either baseline or Grade 1, then dosing may be suspended (until the toxicity resolves to either baseline or at least Grade 1) and the dose of abemaciclib may be reduced as outlined in Table 6.1.1.

If a patient experiences \geq Grade 3 non-hematologic toxicity possibly related to abemaciclib, then dosing must be suspended (until the toxicity resolves to either baseline or at least Grade 1) and the dose of abemaciclib must be reduced as outlined in Table 6.1.1.

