6.3.4 General Guidance for Hepatic Monitoring

Alanine aminotransferase (ALT) and aspartate aminotransferase (AST) elevation are considered expected with the use of abemaciclib. See Table 6.1 for dose modification guidance. Hepatic monitoring should depend upon the severity and persistence of the observed laboratory test abnormalities. If a study patient experiences elevated AST/ALT 5.0xULN and elevated total bilirubin 2.0xULN, or AST/ALT 8.0xULN, liver tests (including ALT, AST, TBL, direct bilirubin, gamma-glutamyl transferase (GGT), and creatinine phosphokinase (CPK), should be repeated within 3 to 5 days to confirm the abnormality and to determine if it is increasing or decreasing. If the abnormality persists or worsens, clinical and laboratory monitoring should be initiated by the investigator, based on the hepatic monitoring tests below:

Table 6.3.4: Hepatic Monitoring Tests for a Hepatic Treatment Emergent Abnormality.

Hepatic Hematology

Hemoglobin
Hematocrit
RBC
WBC
Neutrophils, segmented and bands
Lymphocytes
Monocytes
Eosinophils
Basophils
Platelets

Hepatic Chemistry

Total bilirubin
Direct bilirubin
Alkaline phosphatase
ALT
AST
GGT
CPK

Haptoglobin**Hepatic Coagulation**

Prothrombin Time
Prothrombin Time, INR

Hepatic Serologies^a

Hepatitis A antibody, total
Hepatitis A antibody, IgM
Hepatitis B surface antigen
Hepatitis B surface antibody
Hepatitis B Core antibody
Hepatitis C antibody
Hepatitis E antibody, IgG
Hepatitis E antibody, IgM

Anti-nuclear antibody**Anti-actin antibody****Anti-smooth muscle antibody**

Abbreviations: ALT = alanine aminotransferase; AST = aspartate aminotransferase;
CPK = creatine phosphokinase; GGT = gamma-glutamyl transferase; Ig = immunoglobulin;
INR = international normalized ratio; RBC = red blood cells; WBC = white blood cells.

a Reflex/confirmation dependent on regulatory requirements and/or testing availability

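### Section 6.3.1's rule for Grade 3 or higher toxicity has no exception for the two AST/ALT situations in which Table 6.1 stops abemaciclib

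*Combined protocol and SAP*

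**What the plan says.** Section 6.3.1 covers non-hematologic toxicity, and its heading sets aside only diarrhea. Its last paragraph is mandatory and applies from Grade 3 upward: "Grade 3 non-hematologic toxicity possibly related to abemaciclib, then dosing must be suspended" until the event is back to baseline or Grade 1, "and the dose of abemaciclib must be reduced as outlined in Table 6.1.1". Table 6.1.1 lists four dose levels (200, 150, 100 and 50 mg every 12 hours) and contains no stopping step.

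Table 6.1 treats AST/ALT separately. Its general rows carry the label "Non-hematologic Toxicity (except diarrhea and increased AST/ALT) Section 6.3", so transaminase elevation is taken out of the general rule there. The hepatic rows then give "Discontinue Abemaciclib", with dose reduction marked as not applicable, in two cases:

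- Grade 4 AST/ALT (above 20.0 x ULN).
- Grade 3 AST/ALT (above 5.0 and up to 20.0 x ULN) with total bilirubin above 2.0 x "ULN, in the absence of cholestasis".

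Section 6.3.4 describes AST/ALT elevation as expected with this drug and sends the reader to the table: "See Table 6.1 for dose modification guidance".

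**The concern.** Both stopping events in Table 6.1 are non-hematologic and at least Grade 3. When they are judged possibly related to abemaciclib, they fall within the wording of 6.3.1. That paragraph provides for a hold and a lower dose. The table provides for the end of treatment. The protocol does not say which governs, and 6.3.1 points only to the dose-level table, not to Table 6.1 or to 6.3.4.

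At stake is the handling of a patient with very high transaminases, or with a combined transaminase and bilirubin rise that cholestasis does not explain. An investigator who opened 6.3.1 and followed it could put such a patient back on drug after recovery and believe that the protocol had been followed.

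**Working it through.** No sample size, power or error rate is involved, so the check is a comparison of texts.

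**1. Same event, two instructions** (events possibly related to abemaciclib)

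| Event | Section 6.3.1, read alone | Table 6.1, hepatic rows |
|---|---|---|
| Grade 4 AST/ALT | Hold to baseline or Grade 1; reduce | Discontinue; reduction not applicable |
| Grade 3 AST/ALT, bilirubin above 2.0 x ULN, no cholestasis | Hold to baseline or Grade 1; reduce | Discontinue; reduction not applicable |
| Grade 3 AST/ALT without that bilirubin rise | Hold at once; reduce | Hold and reduce if not resolved within 7 days (natural reading of the row) |

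The first two rows are the point here. In the third, both texts lead to a hold and a reduction and differ only in when the action starts. 6.3.1 is the more cautious.

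**2. Does 6.3.1 except AST/ALT anywhere?** No. The heading names diarrhea. The cycle-start paragraph names alopecia, diarrhea and fatigue. The Grade 2 paragraph names diarrhea and refers to 6.3.2. The Grade 3 or higher paragraph names nothing. Because the section does write out exceptions elsewhere, a reader may take the silence on AST/ALT as deliberate.

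**3. Is the stopping threshold stated anywhere else?**

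- Section 5.5 lists unacceptable adverse events as a reason to come off therapy. That permits stopping by judgement but sets no AST/ALT or bilirubin limit.
- Section 6.3.4 has a trigger at similar values ("If a study patient experiences elevated AST/ALT 5.0xULN and elevated total bilirubin 2.0xULN"), but the action there is to repeat liver tests within 3 to 5 days. Dosing is left to the table.

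The two hepatic rows of Table 6.1 are therefore the only place where these events are tied to discontinuation.

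**4. Would another rule block the restart?**

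- 6.3.1 itself requires recovery to baseline or Grade 1.
- Section 5.2 requires, on day 1 of each later cycle, total bilirubin no higher than 1.5 x ULN and AST/ALT no higher than 3 x ULN (5.0 x ULN with documented liver metastases).

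Both are conditions on current laboratory values. Once the values have recovered they are met, and neither looks back at how severe the episode was. They delay a restart but do not prevent one.

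**5. Can the intended rule be recovered?** Yes. The table's general rows exclude AST/ALT, its hepatic rows cite 6.3.4, and 6.3.4 returns the reader to Table 6.1. Together these point to discontinuation.

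**The case against.** The strongest reply is that the specific rule already governs and is signposted from both ends. The table removes AST/ALT from its general rows, and 6.3.4 names the table as the source for dosing. The heading of 6.3.1 speaks of other non-hematologic toxicity, while AST/ALT has its own subsection. Section 6.3.3 works the same way: it prescribes no dose change for raised creatinine, although 6.3.1 does not exempt creatinine either. So the later subsections of 6.3 seem meant to displace the general paragraph. This stands as evidence of intent and limits the problem to someone who consults 6.3.1 and goes no further. It does not put the exception into 6.3.1, which is mandatory in tone and gives no pointer to either place.

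Two stronger readings are tempting and should not be drawn.

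- A reader might infer that the two instructions are irreconcilable, so that obeying one breaches the other. The text does not go that far. 6.3.1 requires a hold and, if dosing restarts, a lower dose; it never says that treatment must restart. An investigator who discontinues breaches nothing in 6.3.1. The conflict is that 6.3.1 permits what the table forbids.
- A reader might infer that the protocol lacks a hepatic stopping rule, or that recovering patients face uncontrolled re-exposure. Table 6.1 states the rule explicitly, and the recovery conditions in 6.3.1 and 5.2 apply before any restart.

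**Conclusion.** The point holds as a wording conflict with a safety consequence. Section 6.3.1, taken by itself, allows a reduced-dose restart after recovery in exactly two situations where Table 6.1 ends treatment: Grade 4 AST/ALT, and Grade 3 AST/ALT with total bilirubin above 2.0 x ULN without cholestasis.

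Its practical size is small. It depends on one of these events occurring, on its being judged possibly related, and on the investigator relying on 6.3.1 without reading the hepatic rows or 6.3.4. The documents give no frequency for either event, so the number of patients affected cannot be estimated. Nothing in the objectives, endpoints, sample size or analysis changes.

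The conclusion rests on reading 6.3.1 literally and on taking Table 6.1 as the intended rule, which its scope label and 6.3.4 support. The correction is worth making because the paragraph is mandatory, the events are serious, and the remedy costs almost nothing.

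**What to change.** Add an exception clause to the Grade 3 or higher sentence of 6.3.1, for example:

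*except Grade 4 AST/ALT, or Grade 3 AST/ALT with total bilirubin >2.0 x ULN in the absence of cholestasis, for which abemaciclib must be discontinued per Table 6.1 (see Section 6.3.4).*

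Leave the immediate hold for Grade 3 AST/ALT without the bilirubin rise as it is. A blanket AST/ALT exclusion from 6.3.1 would be tidier, but on the natural reading of Table 6.1 it would replace that hold with a 7-day allowance and so relax a safety rule. The narrower clause leaves that difference in timing in place; the sponsor can settle it separately.

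The cost is one wording amendment to one sentence. It uses thresholds already in the protocol, relaxes no safety rule, adds no tests, visits or patients, and leaves the statistical design untouched.

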6.3.2 Diarrhea

A patient experiencing diarrhea requiring hospitalization (irrespective of grade, that is, requiring intravenous [IV] rehydration) or severe diarrhea (Grade 3 or 4) must have study treatment suspended (until the toxicity resolves to either baseline or Grade 1) and should have the study drug dose reduced by 1 dose level as outlined in Table 6.1.

If a patient experiences persistent or recurrent diarrhea that does not resolve with maximal supportive measures within 24 hours to either baseline or at least Grade 1, then study treatment should be suspended (until the toxicity resolves to either baseline or at least Grade 1) and the dose of study drug may be reduced by 1 dose level as outlined in Table 6.1.1 at the discretion of the investigator. If the participant resumes treatment at the same dose level and diarrhea recurs despite maximal supportive measures, the dose of study drug must be reduced by 1 dose level as outlined in table 6.1.1.

6.3.3 General Guidance for Increases in Serum Creatinine and Assessment of Renal Insufficiency

Abemaciclib has been shown to increase serum creatinine due to inhibition of renal tubular transporters without affecting glomerular function (as measured by iohexol clearance). In clinical studies, increases in serum creatinine occurred within the first month of abemaciclib dosing, remained elevated but stable through the treatment period, were reversible upon treatment discontinuation, and were not accompanied by changes in markers of renal function, such as blood urea nitrogen (BUN), cystatin C, or calculated glomerular filtration rate based on cystatin C. Dose modifications are at the discretion of the treating provider, but none are stipulated by this protocol.

6.3.4 General Guidance for Hepatic Monitoring

Alanine aminotransferase (ALT) and aspartate aminotransferase (AST) elevation are considered expected with the use of abemaciclib. See Table 6.1 for dose modification guidance. Hepatic monitoring should depend upon the severity and persistence of the observed laboratory test abnormalities. If a study patient experiences elevated AST/ALT 5.0xULN and elevated total bilirubin 2.0xULN, or AST/ALT 8.0xULN, liver tests (including ALT, AST, TBL, direct bilirubin, gamma-glutamyl transferase (GGT), and creatinine phosphokinase (CPK), should be repeated within 3 to 5 days to confirm the abnormality and to determine if it is increasing or decreasing. If the abnormality persists or worsens, clinical and laboratory monitoring should be initiated by the investigator, based on the hepatic monitoring tests below:

Table 6.3.4: Hepatic Monitoring Tests for a Hepatic Treatment Emergent Abnormality.

Hepatic Hematology

Hemoglobin
Hematocrit
RBC
WBC
Neutrophils, segmented and bands
Lymphocytes
Monocytes
Eosinophils
Basophils
Platelets

Hepatic Chemistry

Total bilirubin
Direct bilirubin
Alkaline phosphatase
ALT
AST
GGT
CPK

Haptoglobin**Hepatic Coagulation**

Prothrombin Time
Prothrombin Time, INR

Hepatic Serologies^a

Hepatitis A antibody, total
Hepatitis A antibody, IgM
Hepatitis B surface antigen
Hepatitis B surface antibody
Hepatitis B Core antibody
Hepatitis C antibody
Hepatitis E antibody, IgG
Hepatitis E antibody, IgM

Anti-nuclear antibody**Anti-actin antibody****Anti-smooth muscle antibody**

Abbreviations: ALT = alanine aminotransferase; AST = aspartate aminotransferase;
CPK = creatine phosphokinase; GGT = gamma-glutamyl transferase; Ig = immunoglobulin;
INR = international normalized ratio; RBC = red blood cells; WBC = white blood cells.

a Reflex/confirmation dependent on regulatory requirements and/or testing availability

